First subject allocated	First subject that was allocated to IMP, a synonym for “first subject entered”.
First subject in	Date of first enrolled subject.
Investigational medicinal product	A generic term describing the preparations under investigation in this trial, i.e., tapentadol PR tablets and morphine PR tablets.
Last subject out	Date of last contact with the last subject according to the protocol.
Modified CAS	Modified constipation assessment scale (questionnaire).
Opioid naïve	No intake of opioids within the 4 weeks prior to enrollment.
Screened subjects	Screened subjects are subjects undergoing screening. Screening is any activity concerning subjects who could potentially be enrolled into the trial before the informed consent form is signed.
Treated subjects	Subjects with at least 1 administration of IMP.
Treatment completers Part 1	Subjects who have completed the 14-day Treatment Period.
Treatment completers Part 2	Subjects who have completed the 12-month Tapentadol Period.
Trial completers Part 1	Subjects who have completed the 14-day Treatment Period and Visit F7D or who entered the Tapentadol Period of Part 2.
Trial completers Part 2	Subjects who fully completed the extension period, i.e., either subjects completing the Tapentadol Period and the follow-up visit (F7D) or subjects completing the Observation Period (F12M) not earlier than 351 days after Visit VE.

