8 TRIAL DESIGN

This is a 2-part trial:

Part 1 is a 14-day (Treatment Period) Phase II/III, randomized, multi-site, open-label, active-controlled, parallel group trial in subjects aged 6 years to less than 18 years, suffering from long-term pain requiring prolonged release opioid treatment. The target is to allocate 69 subjects in a ratio of 2:1 to treatment with tapentadol PR or morphine PR twice daily.

After the Enrollment Visit, subjects complying with the inclusion/exclusion criteria will enter Part 1.

Blood samples for pharmacokinetic evaluations will only be drawn from subjects on tapentadol PR.

Part 1 of the trial will be completed after the last subject has attended Visit VE. Data of Part 1 will comprise the primary analysis of the trial.

Part 2 is an open-label Extension Period with tapentadol treatment (Tapentadol Period) or an observation period without tapentadol treatment (Observation Period) lasting for up to 12 months.

Tapentadol Period (12 months): Subjects completing the Treatment Period (Part 1) and who are still in need of treatment with a prolonged release opioid can enter the Tapentadol Period. They will be treated with tapentadol PR for up to 12 months until Visit F12M (a 12-month visit relative to Visit VE).

Observation Period (12 months): Subjects not completing the Treatment Period (Part 1), but who have taken at least 1 dose of IMP, and those who complete the Treatment Period but do not want to continue with tapentadol PR, will enter the Observation Period (12 months). Subjects will be followed up until Visit F12M to assess any long-term effects after discontinuing treatment with the IMP. Subjects in the Tapentadol Period of Part 2 may stop treatment early (before Visit F12M) and switch to the Observation Period for the remainder of Part 2.

Confidential

Protocol KF5503-66
including Amendment 05

Page 38 of 137
DMS version 9.0
27 Jul 2017

Part 2 of the trial will be completed after the last subject has completed or discontinued from the trial.

Trial population

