11.1.2.4 Visit F12M (at 12 months after Visit VE, range ± 14 days)

The following procedures will be performed:

- Record concomitant medication intake/therapies.
- Perform a physical examination, document that it was performed, and record changes to previous assessment.
- Record height.
- Record body weight.
- Record vital signs (respiratory rate, systolic and diastolic blood pressure, and pulse rate).
- Complete the following questionnaires:
 - Modified CAS questionnaire.
 - Dispense SOWS questionnaire for completion at home if this is the visit of the last intake of IMP. To be completed once daily until the seventh day after the last intake of IMP. To be collected at Visit F7D.
- Record “pain right now” in the CRF (VAS and FPS-R).
- Take blood for central laboratory (hematology, clinical chemistry).
- Collect urine/perform dip stick urinalysis.
- Perform a urine pregnancy test in female subjects who are post-menarchal or older than 12 years at the time of the scheduled visit.
- Check diary compliance.
- Collect the diary if IMP has been stopped at this visit, if not already collected.
- Collect returned IMP.
- Perform drug accountability:
 - Confirm and document compliance with IMP intake.
 - Verify discrepancies with subject, or parent(s), legal guardian(s), or caregiver.
- Assess and record adverse events.

11.1.3 Visit F7D (Final post treatment visit, at 7 days after stopping IMP, range ± 2 days)

Visit F7D is the final post treatment visit, performed 7 days (± 2) after stopping IMP, i.e., after Visit F12M, or after Visit VE for subjects stopping IMP in Part 1, or Visit ET for subjects stopping IMP before Visit F12M in Part 2.

The following procedures will be performed:

- Record concomitant medication intake/therapies.
- Perform a physical examination, document that it was performed, and record changes to previous assessment.
- Record vital signs (respiratory rate, systolic and diastolic blood pressure, and pulse rate).
- Collect the completed SOWS questionnaires.
- Assess and record adverse events.

Confidential

Protocol KF5503-66
including Amendment 05

Page 67 of 137
DMS version 9.0
27 Jul 2017

- Complete end of trial tasks, e.g., collect subject trial cards (if the subject is discontinuing from the trial).

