- Analysis of exposure adjusted incidence rates was limited to TEAEs of the Tapentadol Period:
 - Due to the short treatment duration of 14-days only and very low rate of discontinuations during the Treatment Period
 - And as AEs assigned to the Observation Period are not considered treatment-emergent. Furthermore, the presentation of confidence intervals for the difference in incidence rates was discarded due to the reduced sample size and the following limited value of information.
- A summary of the height Z-Scores was added to Part 2. Converting heights to Z-score allows for a comparison of heights across ages and sexes and therefore better evaluation over time.
- Description of the multiple imputation approach was improved to provide clearer programming instructions.

Some further minor adaptations (e.g. adding further details or clarifications to individual analyses, rewordings) and minor editorial changes (e.g., the correction of typing errors or format changes) are not specified here.

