8 ANALYSIS CONVENTIONS

8.1 General principles

Analysis structure

Separate analyses will be performed for Part 1 and Part 2.

The analysis for Part 1 will take into consideration the Treatment Period of Part 1. For Part 1, all presentations will be done per treatment arm, i.e., comparing the tapentadol arm to the morphine arm.

The analysis for Part 2 will take into consideration the Tapentadol Period and Observation Period of Part 2. Given that the different periods, i.e., Tapentadol Period and Observation Period, are not comparable, due to the heterogeneity of the populations (see Section 18.1.3 for additional information), all analyses of Part 2 will be illustrated separately for the Tapentadol and Observation Period as detailed below, if not specified differently.

For the Tapentadol Period, all statistical analyses will be presented by the following arms:

- Subjects in the Tapentadol Period pretreated with morphine during Part 1.
- Subjects in the Tapentadol Period pretreated with tapentadol during Part 1.
- All subjects in the Tapentadol Period.

For the Observation Period, all statistical analyses will be presented by the following arms:

- Subjects pretreated with morphine during Part 1 and continuing the trial in the Observation Period directly after Part 1.
- Subjects pretreated with tapentadol during Part 1 and continuing the trial in the Observation Period directly after Part 1.
- All subjects continuing the trial in the Observation Period directly after Part 1.
- Subjects discontinuing the Tapentadol Period before F12M and continuing the trial in the Observation Period.

Unless otherwise specified, descriptive summaries will be provided for each time point and for the change from baseline (defined in Section 8.2.2) to each time point. Additionally, for Part 2, the last assessment (defined in Section 8.2.2) and change from baseline to the last assessment will be summarized.

Data presented in subject data listings will be sorted by treatment if not specified differently.

Unscheduled measurements of laboratory parameters, vital signs and electrocardiogram will be presented in the subject data listing. In general, unscheduled measurements will not be included in the analysis. However, they will be considered in the derivation of the overall post-baseline value (see Section 18.1.12.1) that is used in the shift and alert frequency analyses.

Details on the programmatic derivation of the trial periods can be found in Section 18.1.2.10.

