8.2.2 Further definitions

Term	Part/Period	Definition
Pre-treatment-period	-	Before first IMP administration (excluded)
Therapeutic reach	-	
The therapeutic reach is the time after the last IMP intake that a subject is still considered to be potentially affected by a study drug.
 
For tapentadol PR and morphine PR, the therapeutic reach is defined as 72 hours after (last) IMP intake.

On-treatment-period	Part 1	
 • Subjects continuing in the Tapentadol Period after the Treatment Period: 
 a. Start: First IMP administration of Part 1 (included) b. End: 
 i. If the last administration of IMP during Part 1 is more than 3 days before Visit VE: Last administration of IMP during Part 1 + 72 hours (included, therapeutic reach) ii. If the last administration of IMP during Part 1 is less than 3 days before Visit VE: Visit VE (included) c. Start: First IMP administration (included) d. End: Last administration of IMP during Part 1 + 72 hours (included)
	Part 2	
Tapentadol Period only:
 
 a. Start: Visit VE (excluded in case VE is included in the on-treatment period of Part 1; included in case VE is not included in the on-treatment period of Part 1) b. End: Last administration of IMP during the Tapentadol Period + 72 hours (included)
Post-treatment-period	-	After last IMP administration drug intake + 72 hours (excluded)
Enrolled subjects	-	Informed consent form signed. If required by local law an assent form signed.
Treated subjects	-	Subjects with at least 1 administration of IMP.
Treatment completers	Part 1	
Subjects who have completed the 14-day Treatment Period.
 
Completion of the 14-day Treatment Period means that a subject performs the End of Treatment Visit (Visit VE) in the allowed window of 15 ± 1 days, i.e., at or later than Day 14, and has the last IMP intake of part 1 no earlier than Day 13 in the evening.

	Part 2	
Subjects who have completed the 12-month Tapentadol Period.
 
Completion of the 12-month Tapentadol Period means that a subject performs the 12-month follow-up visit (F12M) in the window of 365 ± 14 days, i.e., at or later than 351 days after Visit VE, as part of the Tapentadol Period.

Trial completers	Part 1	Subjects who have completed the 14-day Treatment Period and who performed Visit F7D or entered the Tapentadol Period of Part 2.

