- Pre-treatment (Part 1 only, all enrolled subjects, by treatment arm and overall)
 - Non-TEAE.
 - Serious non-TEAE.
- Post-treatment (all trial Periods together, SAF, presenting the arms of the Observation Period)
 - Non-TEAE.
 - Serious non-TEAE.

Percentages will be calculated related to the total number of subjects/events presented in the respective table as outlined above for the TEAE tables by SOC and PT.

Analysis by System Organ Class, Preferred Term and descriptors

For Part 1 and the Tapentadol Period of Part 2, the number and percentage of events will be summarized by SOC and PT (sorted alphabetically) for the following AE descriptors. Presentations will be for TEAEs only.

- Intensity: mild, moderate, severe.
- Causal relationship to the IMP: related (with subcategories: possible, probable/likely, certain), not related (with subcategories: not related, unlikely), unknown (with subcategories: conditional/unclassified, assessable/unclassifiable, causal relationship missing).
- Outcome: recovered/resolved, recovering/resolving, not recovered/not resolved, recovered/resolved with sequelae, fatal, unknown.
- Non IMP related countermeasures: none, newly started medication, trial discontinuation, others.
- Action taken with IMP: dose increased, dose reduced, drug interrupted, drug withdrawn, dose not changed, not applicable, unknown.
- Measures of location and variation will be calculated for:
- Duration of TEAEs: Duration will be analyzed in days with measures of dispersion and variation.
- Time to onset of TEAE will be analyzed in days with measures of dispersion and variation.

Denominator for percentage calculation will be the number of all TEAEs for presentation over all SOCs, and the number of TEAEs per SOC or PT respectively for the presentation per SOC and PT, respectively.

The number and percentage of all post-treatment non-TEAEs (all Periods together) will be summarized by SOC and PT (sorted alphabetically) for the following AE descriptors:

- Intensity.
- Time to onset of post-treatment non-TEAEs after last IMP administration will be summarized with measures of dispersion and variation.

Listings

The following listings will be produced for all enrolled subjects:

- Deaths.
- Serious adverse events other than death.
- AEs leading to discontinuation from the trial.
- AEs leading to discontinuation from IMP.
- AEs leading to IMP dose decrease or interruption of IMP.

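### Post-treatment adverse event tables give crude incidence over very unequal follow-up, and have no column for children who complete the Tapentadol Period or who leave the trial

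*SAP*

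**What the plan says.** SAP 8.2.2 starts the post-treatment period 72 hours after the last dose: "After last IMP administration drug intake + 72 hours (excluded". Events up to that point are treatment-emergent. Later ones are post-treatment non-TEAEs.

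SAP 15.1.2.2 summarises non-TEAEs and serious non-TEAEs of that period by system organ class and preferred term, with the layout "Post-treatment (all trial Periods together, SAF, presenting the arms of the Observation Period". No overall column is named, although the pre-treatment tables in the same list have one.

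SAP 8.1 defines four Observation Period arms. Three cover children who enter observation straight from Part 1: previously on morphine, previously on tapentadol, and both together ("All subjects continuing the trial in the Observation Period directly after Part 1"). The fourth is "Subjects discontinuing the Tapentadol Period before F12M and continuing the trial in the Observation Period".

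Protocol section 3 separates the two ways of completing Part 2: "either subjects completing the Tapentadol Period and the follow-up visit (F7D) or subjects completing the Observation Period (F12M". On F7D, Protocol 11.1.3 says: "Visit F7D is the final post treatment visit, performed 7 days (± 2) after stopping IMP".

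SAP 15.1.2.2 defines the incidence rate as subjects with the event divided by all subjects in the arm. SAP 15.1.2.3 adds an exposure-adjusted rate, but only for TEAEs of the Tapentadol Period. One of the two reasons given in SAP 7.2.2 is: "And as AEs assigned to the Observation Period are not considered treatment-emergent".

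**The concern.** There are two separate faults in one pair of tables.

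First, the tables are set on the Safety Set, which is every treated child, but their columns cannot hold the whole Safety Set. Followed as written, the layout leaves out children who complete the Tapentadol Period and treated children who never enter observation.

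Second, the columns that do exist combine very different lengths of follow-up. Protocol section 8 gives the purpose: "Subjects will be followed up until Visit F12M to assess any long-term effects after discontinuing treatment with the IMP". The natural use of the table is to compare children who stopped after 14 days with children who stopped after longer tapentadol use. F12M is dated from Visit VE, and a child who switches keeps the same trial day number (Protocol 11.1.4), so time off drug is whatever remains of the 12 months. A crude proportion then mixes risk with length of observation.

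SAP 15.1.2.3 introduces the exposure-adjusted rate because early discontinuation makes the crude rate hard to interpret on treatment. Calling later events non-treatment-emergent does not remove that difficulty off treatment.

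**Working it through.** The plan states no figure for this point, so there is none to reproduce. The check places each group in the table and then computes its time at risk.

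**Who has a column**

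- Enters observation directly after Part 1: yes (arms 1 to 3).
- Stops in the Tapentadol Period before F12M and continues in observation: yes (arm 4).
- Completes the Tapentadol Period, then has F12M and F7D: no.
- Is treated, stops IMP and leaves the trial without entering observation: no.

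**Completers' window.** F7D falls on day 7 ± 2 after the last dose (Protocol 11.1.3), and the first 3 days count as on-treatment (SAP 8.2.2). The window is 7 − 3 = 4 days, with a range of 5 − 3 = 2 to 9 − 3 = 6.

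**Time at risk in the displayed arms.** F12M is at day 365 ± 14 (schedule of events, SAP 5.1). Days count from the last dose in Part 1. The formula is: days at risk = F12M day − day of last dose − 3.

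| Child | Calculation | Days |
|---|---|---|
| Direct entrant who stays to F12M | 365 − 0 − 3 | 362 (348 to 376) |
| Switcher, last dose day 84 (TP3) | 365 − 84 − 3 | 278 |
| Switcher, last dose day 252 (TP9) | 365 − 252 − 3 | 110 |
| Switcher, last dose day 336 (TP12) | 365 − 336 − 3 | 26 |

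A very late switcher, with last dose on day 345 and F12M on day 351, has 351 − 345 − 3 = 3 days.

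**Effect on crude incidence.** The documents give no event rate, so a constant rate *h* of first events per subject-year, the same for every child, is assumed. Crude incidence = 1 − exp(−*h* × days / 365.25). For *h* = 1 and 362 days this is 1 − exp(−0.991) = 62.9%.

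| *h* (per year) | 362 days | 278 days | 110 days | 26 days |
|---|---|---|---|---|
| 0.25 | 21.9% | 17.3% | 7.3% | 1.8% |
| 1 | 62.9% | 53.3% | 26.0% | 6.9% |
| 2 | 86.2% | 78.2% | 45.2% | 13.3% |

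Within each row the risk is identical, and only the length of observation changes.

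**The case against.** A reader might infer that completers' post-treatment events are never reported. The documents do not support that. Protocol 14.2.7.1 has all adverse events listed, with non-TEAEs listed separately, and the SAP lists deaths and serious events for all enrolled subjects. SAP 15.1.2.2 also plans a summary by intensity and time to onset of all post-treatment non-TEAEs, all periods together. It names no arms, so completers may be in it. Their gap is about 4 days each, and withdrawal symptoms over those days are captured by the SOWS (SAP 15.2.9). A separate shell document (SAP 18.3) might also add a column. All of this stands, and it makes the missing columns a minor fault. It does not give completers a place or a denominator in the incidence tables as specified.

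A reader might also infer that children who stop later will look safer. That holds only at equal event rates. SAP 18.1.3 says children enter observation for opposite reasons, improvement or worsening disease, so rates may well differ. Direct entrants can also leave early at Visit OPx, which shortens their follow-up. Safety is descriptive with no tests between arms (SAP 15), and limiting the exposure-adjusted rate was a documented choice. These points rule out predicting the direction of the result. They do not make the crude proportions comparable, and the time-to-onset summary shows when events occurred but not how many children were still being followed.

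Finally, a subject-year rate for completers would do harm. With 15 completers (assumed), 15 × 4 = 60 days, or 0.16 subject-years, so one event would read as about 6 per subject-year. This objection stands, and the fix allows for it.

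**Conclusion.** The point holds, as an inexpensive improvement to the safety reporting. Two groups of treated children have no column in the post-treatment incidence tables. For completers, this costs nominally 4 days each (2 to 6) in those tables, while the listings keep their events.

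Unequal follow-up matters more. Time at risk runs from about 362 days for direct entrants who stay to F12M down to 26 days or fewer for late switchers, and only crude incidence is planned. At equal risk, children who stop later would look safer only because they were watched for less time. At 1 first event per subject-year the contrast between 362 and 26 days is about 63% against 7%. At 0.25 it is 22% against 2%, and at 2 it is 86% against 13%.

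The follow-up days come from the documents' visit schedule and assume that children stay to F12M. The event rates, their constancy and their equality across children are assumptions. The primary analysis and the TEAE tables are unaffected.

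**What to change.** In SAP 15.1.2.2:

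1. Add to the post-treatment tables a column for Tapentadol Period completers and one for treated subjects who do not enter observation, or at least a Safety Set total.
2. For each Observation Period arm, give total subject-years and an exposure-adjusted rate beside the crude rate. Run the clock from last IMP + 72 hours to the first event or last contact. Show the number still followed at 1, 3, 6 and 9 months.
3. For completers, give counts and days of follow-up only.
4. State which denominator each percentage uses. The section defines the incidence rate on all subjects in the arm, but also relates table percentages to the subjects or events presented.

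The cost is SAP wording, slightly more programming and one wider table shell. The dates and events needed are already collected.

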15.1.2.3 Exposure adjusted incidence rate

To overcome the difficulties of interpreting the incidence rate in the presence of subjects who prematurely discontinue in the Tapentadol Period of the trial, the exposure-adjusted incidence rate (EAIR) will be used (Siddiqui 2009) in addition to the CIR.

The EAIR is defined as the number of subjects x with a specific TEAE during the period of interest divided by the total exposure time T (in years) in the respective trial group. The exposure time of a subject is the period the subject is at risk to experience the respective TEAE for the first time. It starts at the time-point of first intake of IMP and lasts until occurrence of the first event in the period of interest or is censored at the end of the period of interest of the subject in case of no event. The total exposure time T is defined as the sum of exposure times over all subjects in the respective treatment arm.

The EAIR is interpreted as the number of events occurring per unit time, i.e., subject years in this trial.

For TEAEs of the Tapentadol Period with a CIR of at least 5% in either arm defined in Section 8.1, the point estimates of the EAIR and CIR will be presented for each arm. Sorting will be by PT.

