18.1.2.11 First and last IMP intake

The first and last IMP intake of the Treatment Period and of the Tapentadol Period will be specified based on the start and end dates provided on the IMP dispense form of the eCRF, supported by the eDiary data.

First IMP intake of the Treatment Period

The first IMP intake of the Treatment Period will be the date and time of the day (morning/evening) of the earliest start entry in the eCRF for the Treatment Period.

The time will be set to the time of the corresponding eDiary entry at that date and time of the day if available; else the time will be missing.

First IMP intake of the Tapentadol Period

The first IMP intake of the Tapentadol Period will be the date and time of the day of the earliest start entry in the eCRF for the Tapentadol Period.

The time will be set to the time of the corresponding eDiary entry at that date and time of the day if available; else the time will be missing.

Last IMP intake of the Treatment Period

The last IMP intake of the Treatment Period will be the date and time of the day of the latest end entry in the eCRF for the Treatment Period.

The time will be set to the time of the corresponding eDiary entry at that date and time of the day if available; else the time will be missing.

Last IMP intake of the Tapentadol Period

The last IMP intake of the Tapentadol Period will be the date and time of the day of the latest end entry in the eCRF for the Tapentadol Period.

The time will be set to the time of the corresponding eDiary entry at that date and time of the day if available; else the time will be missing.

In case the required information from the IMP Dispense form of the eCRF is not available, the first and last IMP intake assigned to the Treatment and Tapentadol Period in the eDiary will be used. In case the switch of the eDiary from the Treatment Period to the Tapentadol Period was missed, the date of Visit VE will be used for the last IMP intake of the Treatment Period and the first IMP intake of the Tapentadol Period, with time of the day and time missing.

18.1.3 Population heterogeneity during Part 2

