18.1.11.7 Time to onset of AE

Time to onset will be calculated based on first administration of IMP. Time to onset of AE will be calculated based on the imputed value for AE start date. In case the time of first administration of IMP is missing, time equal “00:00” will be used for calculation.

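### SAP 15.1.2.3 defines exposure as time at risk but starts the clock at first IMP intake, so the Tapentadol Period EAIR, read literally, includes about 14 Part 1 days in which no counted event can occur

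*SAP*

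**What the plan says.** SAP 15.1.2.3 adds the EAIR to the crude incidence rate (CIR) because early discontinuation in the Tapentadol Period makes the CIR hard to interpret. The EAIR is the number of subjects with a given TEAE divided by the summed exposure time in years. Exposure time is described in three ways:

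- the concept: "The exposure time of a subject is the period the subject is at risk to experience the respective TEAE for the first time";
- the start, and the end when there is an event: "It starts at the time-point of first intake of IMP and lasts until occurrence of the first event in the period of interest";
- the end when there is no event: it "is censored at the end of the period of interest of the subject in case of no event".

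Reporting is confined to Part 2: "For TEAEs of the Tapentadol Period with a CIR of at least 5% in either arm". The amendment rationale in SAP 7.2 agrees: "Analysis of exposure adjusted incidence rates was limited to TEAEs of the Tapentadol Period".

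For the Tapentadol Period, the on-treatment window in SAP 8.2.2 that decides which TEAEs count opens with "Start: Visit VE (excluded in case VE is included in the on-treatment period of Part 1". SAP 18.1.2.11 also defines a period-specific start of dosing: "The first IMP intake of the Tapentadol Period will be the date and time of the day of the earliest start entry". SAP 15.1.2.3 does not refer to it.

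On onset, SAP 18.1.11.7 says: "Time to onset will be calculated based on first administration of IMP". SAP 15.1.2.2 tabulates time to onset for Part 1 and for the Tapentadol Period.

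**The concern.** In SAP 15.1.2.3 the counted event and the censoring point both belong to the period of interest, but the start of the clock is tied to no period. If the start is in Part 1, the denominator covers Part 1 plus the Tapentadol Period while the numerator covers the Tapentadol Period only. The added days can only lower the rate.

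IMP includes morphine PR (Protocol Section 3), and SAP 8.1 presents morphine-pretreated subjects as a separate Tapentadol Period arm. In that arm the extra person-time would not even be tapentadol exposure.

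Long-term safety is the objective of Part 2, and the EAIR is there to handle early stopping. The distortion is largest when mean at-risk time is short, which is the situation the measure was added for.

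**Working it through.** **Step 1. What the unqualified first intake means.** The words *in Part 1* are not in SAP 15.1.2.3; they are inferred from usage elsewhere in the SAP.

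- 18.1.2.4 makes the day of first IMP intake trial Day 1.
- 12.1 uses the bare term in the Part 1 duration formula but names Part 2 in the Part 2 formula.
- 18.1.2.11 and 18.1.4.1 name the Tapentadol Period when its own first intake is meant.

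On this usage, the start rule in 15.1.2.3 points to Part 1.

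**Step 2. Whether Part 1 days can produce a counted event.** Under 8.2.2 the Part 2 on-treatment window opens at Visit VE. An earlier event belongs to Part 1, so those days contribute nothing to the numerator. Subjects may well have TEAEs in Part 1, but these are not counted in this EAIR.

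**Step 3. Size.** The plan states no EAIR, person-time or mean at-risk time, so there is no planned figure to reproduce. Inputs:

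- Offset o = 14 days of Part 1 dosing (Protocol synopsis), with a range of 13 to 15 days from the 14 (± 1) days in Protocol 10.2.2.
- T = mean at-risk days per subject within the Tapentadol Period. This is **assumed**, from 28 to 365 days.

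With x events and n subjects, the matched rate is x/(nT) and the literal rate is x/(n(T+o)). Their ratio is T/(T+o), so the reduction is o/(T+o).

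| Assumed T (days) | 14/(T+14) | Reduction | With o = 13 to 15 |
|---|---|---|---|
| 28 | 14/42 | 33.3% | 31.7% to 34.9% |
| 56 | 14/70 | 20.0% | 18.8% to 21.1% |
| 84 | 14/98 | 14.3% | 13.4% to 15.2% |
| 182 | 14/196 | 7.1% | 6.7% to 7.6% |
| 365 | 14/379 | 3.7% | 3.4% to 3.9% |

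Illustration with assumed n = 40 and x = 4, per year of 365.25 days:

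- T = 28: 4/(40 × 28/365.25) = 1.304 becomes 4/(40 × 42/365.25) = 0.870.
- T = 84: 0.435 becomes 0.373.
- T = 365: 0.100 becomes 0.096.

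**Step 4. T is not time on treatment.** Risk time stops at the first event, so T is shorter than treatment time for common events. A simulation assumed exponential event times at 1 per year, exponential discontinuation, a cut at 365 days and 3 days of therapeutic reach. The reduction was 26.4% with median treatment of 28 days (mean at risk 39.1 days; 14/53.1), 13.3% with 84 days, 9.1% with 182 days and 5.7% with no early stopping.

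**Step 5. Onset.** If the clock in 18.1.11.7 also starts in Part 1, each Tapentadol Period onset time is longer by about 14 days (13 to 15). No rate is affected.

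**The case against.** The best defence is the at-risk sentence just before the start rule. A subject cannot be at risk of a Tapentadol Period TEAE before Visit VE, so that sentence already excludes Part 1. In addition, 18.1.2.11 defines first intake only by period, with no trial-wide version, and 12.1 measures Part 2 exposure from Part 2 dosing. A programmer could well arrive at the right start. This stands as a reason not to say that the reported rates will be too low. It does not clear the text: the concept and the operational rule disagree, and the operational rule is the one likely to be coded.

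The consequence is also limited. SAP 15 plans no tests on safety data. The EAIR is a point estimate shown beside the CIR, and only for TEAEs with a CIR of at least 5%. Both pretreatment arms gain roughly the same offset, so the contrast between them suffers less than the level does, although the offset cancels fully in a ratio only if mean at-risk times are equal. All of this stands.

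A reader might infer that time to onset is equally wrong. The documents do not support that. Tapentadol-pretreated subjects continue on their last Part 1 dose (Protocol 10.2.3.3), so onset counted from first tapentadol intake is a sensible quantity for them. The difficulty is confined to morphine-pretreated subjects.

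**Conclusion.** SAP 15.1.2.3 is internally inconsistent and should be corrected. On the SAP's own usage, its start rule gives a denominator about 14 days per subject too long, and the EAIR is lower by 14/(T+14). The direction does not depend on T; the size does.

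A reader might take the 33% figure as the expected error. It is not: it needs an arm-wide mean at-risk time of 28 days, which no document gives. Protocol 8.4 notes that few subjects in a similarly designed trial stayed on medication beyond a month, but that is another trial. The interim analysis of Part 2 (SAP 6.1) will have shorter follow-up than the final one, so values nearer the upper rows of the table are plausible there. With a full year at risk the effect is about 4%.

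A reader might also think that starting the clock at the first Tapentadol Period intake settles the matter. That intake can fall after Visit VE, where countable events begin, and could leave events before time zero.

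The crude incidence rate, the primary analysis and all tests are untouched. The time-to-onset question is separate and lesser.

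**What to change.** In SAP 15.1.2.3, start exposure at the start of the Part 2 on-treatment period as defined in 8.2.2, including its rule on whether Visit VE itself belongs to Part 1 or Part 2. Numerator and denominator then open at the same point, and the start agrees with the at-risk definition already in the section.

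Separately, in SAP 18.1.11.7, state the reference time for onset of Tapentadol Period TEAEs. For morphine-pretreated subjects use the start of the Tapentadol Period, because counting from first IMP includes about 14 morphine days. For tapentadol-pretreated subjects, first tapentadol intake is acceptable if stated. If the two arms use different reference times, the onset tables should say so.

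The cost is one changed phrase and one added sentence. The dates needed are already derived under the SAP, and no new data are required.
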